Various factors have been reported to contribute to the pathophysiology of PCOS, but due to the heterogeneity of the syndrome, the pathophysiology remains unclear. However, studies emerged on the crucial role of the gut microbiome in human health. Recent studies confirmed that the gut microbiome is altered in women with PCOS compared to healthy women (4-7), and some of these alterations have been linked to the clinical markers of PCOS (4, 5). Different PCOS phenotypes may show different gut microbiome features due to the heterogeneity of this syndrome, which makes it hard to detect the significant changes in the gut microbiome. Age, obesity, androgen status, and insulin resistance or glucose intolerance should all be taken into account while studying the gut microbiome of PCOS patients.

Even though studies have proven that PCOS patients have an altered gut microbiome, the characteristics of microbiome diversity and the specific types of gut bacteria have remained inconsistent. Studies reported on specific alterations of alpha and beta diversity in PCOS patients. Although some studies have shown that decreased alpha diversity and altered beta diversity were associated with PCOS (4, 5, 8), many studies have reported that microbial diversity remained unchanged (9-11).

Studies have investigated correlations between the clinical features of PCOS and the gut microbiome. Features of PCOS such as hyperandrogenism, hirsutism, insulin resistance, and obesity can all have an impact on the gut microbiome to some extent. The decrease in α -diversity has been linked to total testosterone levels and hirsutism (9, 12), and changes in β -diversity were also correlated with hyperandrogenism (5). Also, some even suggested that the hyperandrogenism seen in the PCOS rodent model may affect the gut microbiome independently of diet (13). The role of metabolic factors, such as obesity and insulin resistance, in the PCOS patient's gut microbiome, remains unclear. Although another study showed that obesity itself is linked to a decrease in gut microbial diversity (12), most studies on the gut microbiome in PCOS have included BMI-matched controls to exclude the

influence of body weight. In another study, BMI was found to positively correlate with three bacterial species, while waist-to-hip ratio and fat mass were also found to significantly correlate with the levels of multiple species (9, 12).

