3. STUDY DESIGN

This is a prospective observational case-control study, conducted at the department of Obstetrics and Gynecology (Division of Reproductive Medicine) at the Erasmus University Medical Center Rotterdam. In this study changes of the gut- and vaginal microbiome will be analysed in correlation with PCOS phenotypes.

Patients: women diagnosed by the division of Reproductive Medicine with PCOS in West- or Central Europe*

Sample size: n=50 PCOS overweight/obese and n=50 PCOS lean patients

Moments of inclusion: after PCOS diagnosis/ COLA screening (Cycle disorders, Oligomenorrhea and Amenorrhea screening)

Controls: n=50 overweight/obese and n=50 lean non-PCOS healthy women

Test sample: vaginal swab, stool sample and blood sample

Study period: 1-11-2022 – 1-12-2024

* The diet is strongly associated with the gut microbiome. The reason to only include women from Western and Central Europe, is because these women have a different diet compared to women from Asian, Mediterranean and African countries (recently reviewed in:(23)) . We want to include women who have a Western diet. In addition, the vaginal microbiome is structurally different across ethnicities (24). To avoid getting too small groups in sub-analyses based on ethnicity or diet, we chose to include patients from Western and Central Europe.

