10 STATISTICAL ANALYSIS

10.1 Primary study parameter(s)

Statistical analyses

The statistical analyses will be conducted using the statistical software R.

Continuous variables will be expressed as mean and standard deviation for normally distributed variables, median and interquartile range for not normally distributed variables.

To analyse the association between the gut microbiome and PCOS compared to controls, reads with some level of similarity will be grouped into operational taxonomic units (OTUs). Alpha and beta diversity analyses will be calculated to estimate the abundance and diversity of species within samples.

Alpha diversity comparisons will be analysed with Shannon diversity index and richness as continuous variables. Higher Shannon diversity index is associated with a more diverse and rich vaginal microbiome. It measures the number of species and the differences between species abundances. A logistic regression model will be used to test the changes of alpha diversity in PCOS and non-PCOS women. Same analyses will be conducted for changes of alpha diversity in overweight/obese and lean women with or without PCOS. Linear regression analyses will be conducted to study the correlation between the diversity of the microbiome (Alpha and Beta diversity) and parameters such as hyperandrogenism, rated as serum total testosterone level or Free Androgen Index (FAI). Other PCOS-associated variables included in the univariable linear regression analyses are: hirsutism, acne, BMI, LH/FSH, testosterone, androstenedione. Significant variables from the univariable regression analyses will be tested in a multivariable linear regression model. To correct for multiple testing, Bonferroni's correction will be conducted.

UniFrac will be used to compare the (dis-)similarities among the microbial communities samples (beta-diversity). Unweighted UniFrac analyses is based on presence/absence of difference taxa and abundances and weighted UniFrac will take the abundances of different taxa into consideration. The results from Unifrac analyses will be represented using Principal Coordinate Analysis (PCoA) plots. PCoA plots will represent the dissimilarity of microbiome samples. The PCoA will be based on the overall structure of the gut microbiome in all samples for PCOS and controls.

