10.2 Secondary study parameter(s)

To analyse the association between the vaginal microbiome and PCOS compared to controls, the bacterial taxa will be first classified to the genus level. The relative abundance will be quantified based on each taxa contribution to an individual sample. Operational taxonomic unit (OTU) abundance will be noted for all samples. Alpha and Beta diversity will be calculated. Associations between the vaginal microbiome (Alpha and Beta diversity) and PCOS-associated variables as BMI, hirsutism, acne, testosterone, androstenedione, LH/FSH, insulin, will be tested in a linear regression model.

To investigate the association between the bacterial diversity and markers for gut permeability and inflammation in PCOS patients, a logistic regression model will be used. Leaky gut markers as calprotectin, zonulin, lipopolysaccharide and soluble CD15 and inflammation markers as CRP, IL-22, IL6 and TNF-a will be tested in the logistic regression model. Also the results of the Food Frequency Questionnaire (FFQ) will be analysed in the logistic regression model.

Differences on clinical characteristics and metabolic biomarkers will be evaluated using t-test or a one-way analysis of variance (ANOVA) for normally distributed variables or non-parameter Wilcoxon test for non-normally distributed variables. Two-sided tests will be used, and p-values less than 0.05 will be considered statistically significant.

As for the metabolomic analysis, the raw data will be pre-processed first. Log-transformation and centering are techniques used to make the data normal distributed. To investigate differences between the PCOS and controls, univariate analysis will be performed to examine each metabolite feature separately.

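### Section 10.1 makes adjustment for BMI in the gut-diversity regressions depend on a univariable p-value, and does not name age, insulin resistance or diet as candidates

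*Protocol*

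**What the plan says.** Section 10.1 of the protocol sets out the analysis in this order.

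- Purpose: "Linear regression analyses will be conducted to study the correlation between the diversity of the microbiome (Alpha and Beta diversity) and parameters such as hyperandrogenism". Hyperandrogenism is measured by total testosterone or the Free Androgen Index (FAI).
- Candidates: "Other PCOS-associated variables included in the univariable linear regression analyses are: hirsutism, acne, BMI, LH/FSH, testosterone, androstenedione". With FAI this makes seven.
- Entry rule: "Significant variables from the univariable regression analyses will be tested in a multivariable linear regression model".
- Multiplicity: "To correct for multiple testing, Bonferroni's correction will be conducted". Neither the number of tests nor whether the correction applies to the screening step is stated.

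Section 10.1 gives no entry threshold. The only significance level is in section 10.2: "Two-sided tests will be used", and "p-values less than 0.05 will be considered statistically significant".

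The Summary (Rationale) says: "Age, obesity, androgen status, and insulin resistance or glucose intolerance should all be taken into account while studying the gut microbiome of PCOS patients". Section 3 describes diet as a strong correlate of the gut microbiome and restricts recruitment for that reason. In the analysis sections, insulin is named only for the vaginal model and the food questionnaire only for a logistic model, both in section 10.2. Age is named in neither section.

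On numbers, section 3 gives "Sample size: n=50 PCOS overweight/obese and n=50 PCOS lean patients", plus 50 overweight/obese and 50 lean controls. Section 10.1 does not say whether these regressions use the 100 women with PCOS or all 200.

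**The concern.** Whether a confounder needs adjusting for depends on its relation to exposure and outcome. Whether its own p-value passes a threshold in one sample is a different question. Androgens, BMI and insulin can be expected to correlate, and screening them one at a time has three consequences.

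- A confounder that narrowly misses the cut is left out, and part of its effect is credited to a correlated variable that stayed in.
- A variable whose effect is offset by a correlated one may look null alone and never reach the model that would reveal it.
- The selected model is reported as if it had been fixed in advance, so its estimates and p-values do not reflect the selection.

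The association of the gut microbiome with diagnostic and metabolic characteristics is part of the main objective (section 2) and the main endpoint (section 8.1.1), so this is not a peripheral analysis.

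**Working it through.** The protocol gives no effect size, correlation, power or coverage for these regressions, so there is no figure to reproduce.

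**Inputs.** From the documents: n=100 (PCOS only) or n=200 (all women), seven candidates, two-sided 0.05 (borrowed from section 10.2). Assumed: standardised variables, testosterone–BMI correlation 0.5, and the effects shown below.

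**Step 1: chance that BMI fails the screen.** For a marginal correlation r, by the Fisher z approximation:

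P(drop) = Φ(z − m) − Φ(−z − m), with m = √(n−3) × atanh(r)

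For r=0.20 and n=200, m = 14.04 × 0.2027 = 2.85. At 0.05 (z=1.96) this gives Φ(−0.89) = 19%. If Bonferroni were applied to the screen, 0.05/7 = 0.0071 (z=2.69) gives Φ(−0.16) = 44%.

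| True BMI–diversity r | n=200, 0.05 | n=200, 0.0071 | n=100, 0.05 | n=100, 0.0071 |
|---|---|---|---|---|
| 0.10 | 71% | 90% | 83% | 96% |
| 0.15 | 44% | 72% | 68% | 89% |
| 0.20 | 19% | 44% | 49% | 76% |
| 0.30 | 1% | 5% | 14% | 36% |

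**Step 2: what the screen sees.** With correlation 0.5, each marginal correlation is a variable's own effect plus 0.5 times the other's.

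- (a) Testosterone 0, BMI -0.2: testosterone shows 0 + 0.5×(-0.2) = -0.10; BMI shows -0.20.
- (b) Testosterone -0.25, BMI +0.2: testosterone shows -0.25 + 0.5×0.2 = -0.15; BMI shows 0.2 + 0.5×(-0.25) = 0.075.
- (c) Both -0.2: each shows -0.2 + 0.5×(-0.2) = -0.30.

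In (b), testosterone at 0.15 passes the screen in only 100−68 = 32% (n=100) or 100−44 = 56% (n=200) of studies, which caps its power. If both variables always stay in, the residual variance is 1 − (0.0625 + 0.04 − 0.05) = 0.9475. The standard error is √(0.9475/(0.75n)), that is 0.112 or 0.079. Approximate power is then Φ(0.25/0.112 − 1.96) = 60% or Φ(0.25/0.079 − 1.96) = 88%.

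**Step 3: simulation.** Two predictors, ordinary least squares, entry at p<0.05. Ranges are across repeated runs.

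| Scenario | n | BMI dropped | Coverage of testosterone 95% interval, given entry | Power, screened | Power, both kept |
|---|---|---|---|---|---|
| (a) | 100 | about 50% | about 72% | – | – |
| (a) | 200 | 18–20% | 86–89% | – | – |
| (b) | 100 | about 89% | about 99% | about 32% | about 58% |
| (b) | 200 | about 81% | about 99% | about 56% | about 87% |
| (c) | 100 | about 14% | about 96% | 0.475 | 0.445 |
| (c) | 200 | under 1% | 0.95–0.96 | 0.73–0.745 | 0.73–0.744 |

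In (a) testosterone enters in only about 17% (n=100) or 31% (n=200) of studies. Non-coverage times entry gives the overall false-positive rate: 0.17 × 0.28 = 4.8%, and 0.31 × 0.11 to 0.14 = 3.4% to 4.3%. Both are below 5%.

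**Step 4: all seven candidates.** Over 28 scenarios with varied effects, correlations, n and threshold, coverage given entry ran from 0.27 to 0.99, against 0.945 to 0.954 when all seven were kept. The lowest values come from scenarios with no true effects, where testosterone rarely enters and does so mostly by chance. In the seven-candidate version of (b) at n=200 and p<0.05, coverage was 0.78 instead of 0.99, so the direction of the error depends on the set-up.

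**The case against.** The strongest reply is that the damaging scenarios are chosen. The protocol's introduction cites lower diversity both with higher testosterone and with obesity, so the expected effects run the same way, as in (c). There, at n=200, BMI almost never drops out, and coverage and power are essentially unchanged. This stands. It means that harm is not inevitable; it does not make the rule sound, because the introduction also calls the role of obesity and insulin resistance unclear.

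Three stronger readings are tempting but go too far.

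- A reader might infer that the rule removes BMI. It does not do so as such: BMI is a named candidate and is almost always kept at n=200 and p<0.05 if its marginal correlation is 0.3 or more.
- A reader might infer that intervals come out too narrow or that false androgen associations multiply. Coverage errs in both directions, and (a) shows no overall excess of false positives. The protocol also promises no confidence intervals here; estimates and p-values are what is affected.
- A reader might call this an outright contradiction of the rationale. The design already deals partly with these factors through balanced BMI strata, an age limit, exclusion of diabetes and insulin sensitizers, and recruitment limited by region for diet. That leaves a tension. The strata protect the PCOS-versus-control contrast; they do not remove BMI from a regression of diversity on testosterone or FAI.

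The reply that a statistical analysis plan could settle this has little force, since the protocol already fixes the entry rule.

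**Conclusion.** The point holds in a limited form. Section 10.1 lets a p-value decide whether body weight is adjusted for and leaves age, insulin resistance and diet outside the named candidates, which fits poorly with the protocol's own rationale.

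The possible loss ranges from almost none (same-direction effects, n=200) to roughly 26 to 31 percentage points of power for testosterone (58−32 and 87−56, opposing effects). Where BMI alone acts at -0.2, it goes unadjusted in about half of studies at n=100 or a fifth at n=200. All of this rests on assumed effects, a correlation of 0.5 and entry at p<0.05. A Bonferroni threshold at the screen would drop BMI more often.

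The finding concerns the linear regressions on PCOS characteristics, which belong to the main objective. A reader might extend it to the PCOS-versus-control comparison of alpha diversity, but that is a separate logistic model to which the screening sentence does not apply.

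**What to change.** Delete the screening sentence in section 10.1 and replace it as follows.

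- For each characteristic of interest (testosterone or FAI, hirsutism, acne, LH/FSH, androstenedione), fit a linear model of diversity with a pre-specified adjustment set: age, BMI, diet from the food questionnaire, and one insulin-resistance measure. Keep the set whatever its p-values.
- Do not put testosterone and FAI in the same model.
- Keep a separate model for each listed characteristic. A single model with one androgen would lose the other diagnostic features in the main objective.
- Apply Bonferroni to these pre-specified tests and state their number.
- Report univariable results as descriptive only.

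No new data are needed: age and BMI are extracted from the clinical file (section 12.1), and hormones, insulin, glucose and the food questionnaire are in section 8.3. The cost is a wording change, a few degrees of freedom and, where effects run in the same direction, slightly lower power at n=100 (0.445 against 0.475 in scenario (c)).

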- To analyse the difference in gut- and vaginal microbiome composition between overweight/obese and lean (with/without PCOS).
- To analyse potential metabolic profiles characterizing different phenotypes of PCOS

Study design: A prospective observational case-control study, conducted at the Department of Obstetrics and Gynecology (Division of Reproductive Medicine) at the Erasmus University Medical Center Rotterdam

Study population: Patients with PCOS diagnosed based on the Rotterdam criteria must be Caucasian women, aged 18 - 45 years old (premenopausal), either overweight or obese (BMI>25) or lean (BMI18-25).

Main study parameters/endpoints:

The main parameter of this study is the differences in community structure (presence or absence of bacteria, alpha, and beta diversity) of the gut microbiome between PCOS patients and controls.

Secondary study parameters: 1. Differences in community structure (presence or absence of bacteria, alpha, and beta diversity) in the *vaginal* microbiome between PCOS patients and controls. 2. The differences and similarities between the vaginal- and gut microbiome composition in PCOS patients 3. The differences and similarities between the vaginal- and gut microbiome composition between overweight/obese and lean patients (with/without PCOS). 4. Metabolic profiles from different phenotypes of PCOS

Nature and extent of the burden and risks associated with participation, benefit, and group relatedness:

For all participants, the risks involve primarily the burden of participating in a study, which in the current study proposal means 1 additional hospital visit and assessments. Women from the study group have already undergone the regular physical examination (transvaginal ultrasound) and laboratory tests for the standard outpatient clinic for COLA (Cycle disorders, Oligomenorrhea and Amenorrhea) screening. Patients will be asked to collect a stool sample at home and bring or send this to the hospital. A vaginal sample will be obtained by a physician without using a speculum. The risks of participation are considered to be minor and there are no obvious risks associated with participation in the study. The assessment and determination of relevant gut and vaginal microbiome may lead to a better understanding of

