8 METHODS

8.1 Study parameters/endpoints

8.1.1 Main study parameter/endpoint

- Differences in community structure of the gut microbiome between PCOS patients and controls as such and its diagnostic and metabolic characteristics.

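### Section 10.1 applies one Bonferroni correction of unstated scope to a mix of main contrasts, weight-group contrasts and trait regressions; Holm within three named families would be at least as powerful and would fix the main threshold

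*Protocol*

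**What the plan says.** The Summary defines the main parameter as "differences in community structure (presence or absence of bacteria, alpha, and beta diversity) of the gut microbiome between PCOS patients and controls". Section 8.1.1 words it as "Differences in community structure of the gut microbiome between PCOS patients and controls as such and its diagnostic and metabolic characteristics". Neither names a lead measure.

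Section 10.1 turns this into four measures:

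- **Alpha diversity.** "Alpha diversity comparisons will be analysed with Shannon diversity index and richness as continuous variables". For the group comparison, "A logistic regression model will be used to test the changes of alpha diversity in PCOS and non-PCOS women".
- **Beta diversity.** UniFrac is used unweighted and weighted. For the group comparison the section says "The results from Unifrac analyses will be represented using Principal Coordinate Analysis (PCoA) plots". No test is named.

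The alpha-diversity paragraph goes on to two further sets of tests:

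- **Weight groups.** "Same analyses will be conducted for changes of alpha diversity in overweight/obese and lean women with or without PCOS".
- **Traits.** Linear regressions of alpha and beta diversity on total testosterone, Free Androgen Index, hirsutism, acne, BMI, LH/FSH and androstenedione. Significant variables then go into a multivariable model.

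The paragraph ends with "To correct for multiple testing, Bonferroni's correction will be conducted". No family or number of tests is attached, and the UniFrac paragraph comes after it. The two-sided 0.05 level is stated only in section 10.2.

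**The concern.** The position of the Bonferroni sentence allows two readings. It may refer only to the trait regressions that come just before it, or to everything in the paragraph. On the first reading the main contrasts are uncorrected although there are several of them. On the second, the main contrasts pay for every trait regression. The threshold for the study's main conclusion therefore depends on a reading that could be settled after the p-values are known. The Introduction already calls earlier diversity findings inconsistent and gives differences in analytical methods as one reason, so this choice should be closed beforehand.

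Whichever reading is meant, a method with the same error control and at least the same power is available at no cost in assumptions.

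**Working it through.** **Inputs.**
- 100 women with PCOS and 100 controls (section 4.4).
- Two-sided level 0.05 (section 10.2).
- Two alpha measures, two UniFrac measures and seven distinct traits (section 10.1).
- Section 4.4 gives no effect size, SD or power, so there is no planned figure to reproduce. Standardised differences of 0.3, 0.4 and 0.5 are assumed. Power is that of a two-sample t-test on one diversity measure, used as an approximation to the logistic-regression test.

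**Reading 1: the correction covers only the traits.** For m independent tests the family error is 1 − 0.95^m. Simulation with correlated normal statistics gives the other column.

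| Main tests at 0.05 | Independent | Correlation 0.5 |
|---|---|---|
| 2 (Shannon, richness) | 1 − 0.95² = 9.75% | 9.1% |
| 4 (UniFrac measures also tested) | 1 − 0.95⁴ = 18.5% | 15.6% |

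At correlation 0.8 the figures are about 7.9% and 11.4%.

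**Reading 2: the correction covers the whole paragraph.** The alpha-diversity tests number 2 (PCOS) + 2 (weight group) + 7 × 2 (traits) = 18, so the level is 0.05/18 = 0.0028.

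| Assumed difference | Power at 0.05 | Power at 0.05/18 |
|---|---|---|
| 0.3 SD | 56% | 19% |
| 0.4 SD | 80% | 42% |
| 0.5 SD | 94% | 69% |

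Eighteen is not the largest possible count. The trait regressions are also planned for beta diversity. With all four measures there, the count is 2 + 2 + 7 × 4 = 32, and power at 0.4 SD is about 36%.

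**A family limited to the main contrast.** At 0.4 SD, per-test Bonferroni power is about 71-72% for two tests (level 0.025) and 62% for four (level 0.0125).

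**Holm against Bonferroni.** Simulated with four tests, each 0.4 SD, correlation 0.5, 100 per group:

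| | Bonferroni | Holm |
|---|---|---|
| Power per test | 63% | 72% |
| At least one rejection | 89% | 89% |

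The second row is equal because Holm's first step uses the Bonferroni threshold.

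**The case against.** **The number of tests in a family is often left to a statistical analysis plan, and one may exist.** That stands as far as the count goes. But section 10.1 itself names the correction and places it after a mixture of tests, so the sentence to change is in this document.

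Four stronger readings are tempting and are not supported.

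- **A reader might infer that the main claim has a 19% false-positive risk.** That needs four independent tests at 0.05. The protocol names a PCOS-versus-control test only for Shannon and richness, which gives at most about 10%. UniFrac results are only plotted. Presence or absence of bacteria is not clearly a fifth test either, since section 10.1 ties it to unweighted UniFrac.
- **A reader might infer that the correction halves the power.** That needs both an assumed difference near 0.4 SD and a family that includes the trait regressions. A family of four costs about a quarter (80% to 62%). Under a rule that one rejection among the two alpha tests is enough, power at 0.4 SD and correlation 0.5 falls from 92% to 60% with 18 tests, about a third.
- **A reader might infer that Bonferroni is wrong.** It controls the error validly. It is dominated by Holm for claims about individual measures, and the two give the same answer to whether at least one test rejects.
- **A reader might call the trait regressions exploratory.** Section 2 and section 8.1.1 put diagnostic and metabolic characteristics in the main objective and the main endpoint. They can be corrected separately, but they should not be demoted.

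**Conclusion.** The point holds in a limited form. Section 10.1 states one correction without saying what it covers, in a paragraph that mixes three kinds of question. Depending on the reading, the main contrast has 9-10% family error on the two tests actually named (16-19% if both UniFrac measures are tested), or its per-test power drops to 19 / 42 / 69% at 0.3 / 0.4 / 0.5 SD. The error figures assume correlations from 0.5 down to none and would be lower for more strongly related measures. The power figures rest on assumed effects and on a count of 18.

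A separate limit concerns interpretation. The hypothesis in section 1 is that diversity is lower in PCOS. A UniFrac difference would show that composition differs, not that diversity is lower, so it cannot by itself support that hypothesis.

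**What to change.** In section 10.1, replace the Bonferroni sentence by Holm's procedure at two-sided 5%, applied separately to three families:

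1. **PCOS versus control, gut microbiome:** Shannon and richness. Add weighted and unweighted UniFrac only if a group test is named for them, since PCoA plots are not a test.
2. **Weight-group contrasts.**
3. **Trait regressions.** These stay part of the main objective and are corrected on their own.

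Add that only a rejection for Shannon or richness, in the direction of lower diversity, supports the hypothesis of reduced diversity, and that a UniFrac rejection is reported as a difference in composition.

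The cost is one paragraph, with no added participants or samples. There are two downsides. The smallest main p-value is judged at 0.05/2 = 0.025 with two tests or 0.05/4 = 0.0125 with four. And the 5% error rate holds within each family, not across all of section 10.1, which the text should say.

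### Section 10.1 could use Holm's step-down in place of Bonferroni: same familywise 5% control, never fewer rejections, and a modest gain in power for the trait analyses

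*Protocol*

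**What the plan says.** Protocol section 10.1 plans linear regressions of microbiome diversity on PCOS characteristics. It starts with hyperandrogenism, measured by total testosterone or the Free Androgen Index (FAI), and continues: "Other PCOS-associated variables included in the univariable linear regression analyses are: hirsutism, acne, BMI, LH/FSH, testosterone, androstenedione". Testosterone appears in both places, so the text names about seven distinct traits.

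On the outcome side, "Alpha diversity comparisons will be analysed with Shannon diversity index and richness as continuous variables", which gives two alpha-diversity measures per trait. Beta diversity is to be regressed as well. A second stage follows: "Significant variables from the univariable regression analyses will be tested in a multivariable linear regression model". The paragraph ends with "To correct for multiple testing, Bonferroni's correction will be conducted".

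The number of tests in the family is not stated. The significance level appears only in section 10.2: "Two-sided tests will be used, and p-values less than 0.05 will be considered statistically significant". I assume that it governs section 10.1 too.

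Section 3 plans "n=50 PCOS overweight/obese and n=50 PCOS lean patients" and "n=50 overweight/obese and n=50 lean non-PCOS healthy women", hence 100 patients and 100 controls. Section 4.4 bases these numbers on available samples and published studies, and states no power or effect size.

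**The concern.** Bonferroni compares every p-value with α/m, where m is the number of tests. Holm orders the p-values and compares the smallest with α/m, the next with α/(m−1), and so on, stopping at the first failure. Its first step is the Bonferroni test. Later steps are more lenient, yet the familywise error stays at or below α whatever the dependence between the tests. For deciding which associations are significant, Holm therefore does at least as well on every data set.

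The difference grows with the number of real associations. It has some relevance here because the main objective in section 2 covers the diagnostic and metabolic characteristics of PCOS as well as PCOS itself, and section 1 cites earlier links between diversity and several of the listed traits. What is at stake is limited: some real trait associations could be reported as non-significant when the same data would support them at the same error rate.

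**Working it through.** The plan states no power, family size or adjusted level for these analyses, so there is no figure of its own to reproduce.

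**Inputs**
- From the protocol: about 7 traits and 2 alpha-diversity measures (10.1); two-sided α = 0.05 (10.2); n = 200 if all women are analysed, n = 100 if only patients are (section 3).
- Assumed: m = 7 × 2 = 14 tests; a correlation of r = 0.25 for each real association; four androgen-type traits intercorrelated 0.4; a residual correlation of 0.7 between Shannon index and richness.

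**Step 1: Bonferroni is valid.** The per-test level is 0.05/m, and under independence the familywise error is 1 − (1 − 0.05/m)^m.

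| m | Level per test | Familywise error | Without correction |
|---|---|---|---|
| 7 | 0.00714 | 0.0489 | 0.302 |
| 14 | 0.00357 | 0.0489 | 0.512 |
| 28 (if both UniFrac measures are added) | 0.00179 | 0.0488 | 0.762 |

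**Step 2: Bonferroni power by formula.** Power ≈ Φ(atanh(r)·√(n−3) − z), with atanh(0.25) = 0.2554. For a two-sided level of 0.05/14, z = 2.914.
- n = 200: 0.2554 × √197 = 3.585, and Φ(3.585 − 2.914) = 0.749.
- n = 100: 0.2554 × √97 = 2.516, and Φ(2.516 − 2.914) = 0.345.

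**Step 3: rough ceiling for Holm with four real traits.** These give 4 × 2 = 8 real tests. Leaving aside the small contribution of false rejections, the most lenient level that a real test can meet is 0.05/(14 − 7) = 0.00714, for which z = 2.690.
- n = 200: Φ(3.585 − 2.690) = 0.815.
- n = 100: Φ(2.516 − 2.690) = 0.431.

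Holm's power must lie between the values of steps 2 and 3.

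**Step 4: simulation.** Both procedures were applied to the same 14 Pearson p-values, with 4,000 trials per scenario. The four real traits were the androgen-type ones.

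| Scenario | Average power per real association, Bonferroni v Holm | Gain |
|---|---|---|
| n = 200, 4 of 7 traits real | 74.5% v 78.8% | 4.3 points |
| n = 100, 4 of 7 traits real | 34.6% v 37.6% | 3.0 points |
| n = 200, 1 of 7 traits real | 75.6% v 76.1% | 0.5 points |

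With n = 200 and four real traits, the chance of finding all eight real associations was 30% v 41%, and the familywise error was 1.8% v 3.5%. Holm thus uses more of the permitted 5% without exceeding it.

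**Step 5: other assumptions.** A separate simulation varied r from 0.2 to 0.3, n = 100 or 200, m = 7, 14 or 28, and between-test correlation 0 or 0.5. The gain was 0.4 to 3.7 points with about half of the associations real, and 0.0 to 0.1 points with a single real association. One example is n = 100, r = 0.3, m = 7 and three real: 64.0% v 66.8%. In every replicate Holm rejected all that Bonferroni rejected, and the two methods agreed on whether anything was rejected.

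**The case against.** The strongest reply is that this is a preference. Bonferroni is valid and prespecified, nothing in the protocol contradicts it, and no stated power target is missed. That stands: the point is an optional improvement and corrects no error.

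A reader might also infer that the plan gives up power for nothing. That is too strong. Bonferroni offers simple matching simultaneous confidence intervals and a fixed threshold that does not depend on the other p-values. The protocol promises no simultaneous intervals, however, so little of this would be missed.

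A reader might further infer that most traits are expected to be truly associated, which would make the gain larger: 75.0% v 83.9% with six of seven traits real, and up to 13.3 points in the extreme case that every association is real. The protocol does not support this. Section 1 links alpha diversity to total testosterone and hirsutism, beta diversity to hyperandrogenism, and obesity to lower diversity. That reaches testosterone, FAI, hirsutism and BMI at most. No diversity link is cited for acne, androstenedione or LH/FSH. Section 1 also says that many studies found diversity unchanged and that the role of obesity is unclear, so even four is a favourable count.

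Finally, the simulated family leaves out beta diversity and the multivariable stage, and section 10.1 does not say which tests form the family. Both remarks are right. They limit how far the figures can be trusted, but Holm's advantage over Bonferroni holds for whatever family is fixed. Naming Holm does not define that family.

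**Conclusion.** The point holds as a low-priority improvement. Bonferroni in section 10.1 is sound. Holm gives the same familywise 5% guarantee without further assumptions, never rejects less, and can reject more.

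Assuming 14 tests and real correlations of 0.25, the gain in average power per real association is about 3 points (n = 100) to 4 points (n = 200) if roughly the four traits with cited links are real, and about half a point if only one is. The chance of at least one significant finding does not change. These sizes rest on an assumed family, effect size and correlation structure, because the protocol gives none of them. The ordering of the two procedures does not depend on those assumptions.

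It would be wrong to conclude that real associations will be missed because of Bonferroni. Some could be.

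**What to change.** In section 10.1, replace the Bonferroni sentence with, for example: *Multiple testing is corrected with Holm's step-down procedure (`p.adjust`, `method = 'holm'`) at a two-sided familywise error rate of 5%.* Apply it to the same family of tests that Bonferroni would have covered, and make the change before any data are analysed.

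The cost is a change of wording in the protocol and one argument in R, with no extra participants, samples or assumptions. Because simultaneous intervals that match Holm are less simple, show unadjusted confidence intervals beside the Holm-adjusted p-values and label them as unadjusted.
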